A DLT is defined as any of the following events that occur within 28 days starting with the first dose on C1D1 in the dose escalation cohort and that is considered to be possibly, probably or definitely related to IP. Confirmation of DLTs will be made by the DESC. The severity of AEs will be assessed according to National Cancer Institute's Common Terminology Criteria for Adverse Events (NCI-CTCAE), v5.0. Participants experiencing DLTs, who in the opinion of the investigator are deriving clinical benefit from the study treatment (e.g., marked reduction in tumor burden), may be allowed to continue study treatment with ASP0739 upon resolution of the event to \leq grade 1 or baseline, upon discussion with the sponsor. Participants experiencing DLTs during the single agent dose escalation phase will not be replaced.

DLTs are defined as follows:

- Grade \geq 2 autoimmune reaction
- Grade 3 irAEs that do not resolve to grade \leq 1 in 3 to 5 days
- Grade 4 irAEs
- Grade \geq 3 non-hematological AE that does not resolve to grade \leq 2 within 72 hours of onset
- Grade 4 neutropenia
- Grade 3 febrile neutropenia with or without infection
- Grade 4 thrombocytopenia
- Grade 3 thrombocytopenia accompanied by bleeding that requires any transfusion
- Grade 4 anemia
- Grade 3 anemia requiring transfusion
- AST or ALT $> 5 \times$ upper limit of normal (ULN; grade \geq 3) without liver metastases
- AST or ALT $> 8 \times$ ULN in participants with liver metastases
- AST or ALT $> 3 \times$ ULN and total bilirubin (TBL) $> 2 \times$ ULN (in participants with Gilbert syndrome: AST or ALT $> 3 \times$ ULN and direct bilirubin > 1.5) (confirmed Hy's Law)
- Grade \geq 3 liver function test abnormality lasting \geq 7 days

- Grade 5 toxicity
- Prolonged delay (> 2 weeks) in initiating cycle 2 due to treatment-related toxicity

The following AEs will not be considered DLTs:

- Electrolyte abnormalities that are not associated with clinical sequelae or deemed not clinically significant and corrected with appropriate management or supplementation within 72 hours of onset
- Grade 3 infusion site reaction if successfully managed and resolved within 72 hours of onset
- Alopecia, anorexia or fatigue

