- Grade 3 nausea and/or vomiting if not requiring tube feeding or total parenteral nutrition, or diarrhea and/or constipation if not requiring or prolonging hospitalization that can be managed to grade \leq 2 within 72 hours of onset with standard antiemetic or antidiarrheal medications used at prescribed dose
- Grade 3 liver function test (LFT) elevations that resolve to \leq grade 1 within 7 days; LFT elevations lasting $>$ 7 days that are considered to be clinically significant and at least possibly related to ASP0739 will be considered to be a DLT
- Grade 3 or lower irAEs that resolve to \leq grade 1 within 72 hours of onset after starting treatment including corticosteroids

Participants who are tolerating IP at a dose level that is being reviewed due to the occurrence of DLTs in another participant will not be automatically precluded from continued dosing during the safety review, and will be allowed to continue dosing for as long as tolerated unless directed otherwise as a result of the safety review by the DESC.

DLTs Requiring Discontinuation of Treatment

- If a study participant develops a grade 4 DLT after receiving cycle 1, then the study participant should be discontinued from treatment.
- If a study participant develops a grade \geq 3 non-hematological AE that does not resolve to \leq grade 2 within 72 hours of onset, it should be considered a DLT and the study participant should be discontinued from treatment.
- If there is a delay in administration of the second cycle by $>$ 4 weeks, it would result in discontinuation from treatment after discussion with the sponsor.

ASP0739 in Combination with Pembrolizumab Safety Lead-in

Enrollment in the combination therapy safety lead-in will start once phase 1 single agent dose escalation is completed and the RP2D is defined.

The combination therapy safety lead-in portion will evaluate the RP2D of ASP0739 with a fixed dose of 400 mg pembrolizumab in 6 to 9 participants with at least 6 DLT-evaluable participants. If the RP2D is selected at the same dose level as the MTD based on the phase 1 dose escalation portion, the combination safety lead-in will start at one dose level lower than the MTD.

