Participants experiencing DLTs, who in the opinion of the investigator are deriving clinical benefit from the study treatment (e.g., marked reduction in tumor burden), may be allowed to continue study treatment with ASP0739 upon resolution of the event to \leq grade 1 or baseline, upon discussion with the sponsor. Participants experiencing DLTs during the combination safety lead-in portion will not be replaced.

DLTs are defined as follows:

- Grade \geq 2 autoimmune reaction
- Grade 3 irAEs that do not resolve to grade \leq 1 in 3 to 5 days
- Grade 4 irAE
- Grade \geq 3 non-hematological AE that does not resolve to grade \leq 2 within 72 hours of onset
- Grade 4 neutropenia

- Grade 3 febrile neutropenia with or without infection
- Grade 4 thrombocytopenia
- Grade 3 thrombocytopenia accompanied by bleeding that requires transfusion or hospitalization
- Grade 4 anemia
- Grade 3 anemia requiring transfusion
- AST or ALT $> 5 \times$ ULN (grade ≥ 3) without liver metastases
- AST or ALT $> 8 \times$ ULN in participants with liver metastases
- AST or ALT $> 3 \times$ ULN and TBL $> 2 \times$ ULN (in participant with Gilbert syndrome: AST or ALT $> 3 \times$ ULN and direct bilirubin > 1.5) (confirmed Hy's law)
- TBL $> 3 \times$ ULN (grade ≥ 3)
- Grade ≥ 3 liver function test abnormality lasting ≥ 7 days
- Grade 5 toxicity
- Prolonged delay (> 2 weeks) in initiating cycle 2 due to treatment-related toxicity
- Grade ≥ 2 pneumonitis
- Grade ≥ 2 encephalopathy, meningitis, or motor or sensory neuropathy
- Guillain-Barré syndrome or myasthenic syndrome/myasthenia gravis
- Infusion-related reaction that requires the infusion to be discontinued

The following AEs will not be considered DLTs:

- Electrolyte abnormalities that are not associated with clinical sequelae or deemed not clinically significant and corrected with appropriate management or supplementation within 72 hours of onset
- Grade 3 infusion site reaction if successfully managed and resolved within 72 hours of onset
- Alopecia, anorexia or fatigue
- Grade 3 nausea and/or vomiting if not requiring tube feeding or total parenteral nutrition, or diarrhea and/or constipation if not requiring or prolonging hospitalization that can be managed to grade ≤ 2 within 72 hours of onset with standard antiemetic or antidiarrheal medications used at prescribed dose

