- Grade 3 LFT elevations that resolve to \leq grade 1 within 7 days; LFT elevations lasting > 7 days that are considered to be clinically significant and at least possibly related to ASP0739 and/or pembrolizumab will be considered to be a DLT
- Grade 3 or lower irAEs that resolve to \leq grade 1 within 72 hours of onset after starting treatment including corticosteroids

Participants who are tolerating ASP0739 and/or pembrolizumab at a dose level that is being reviewed due to the occurrence of DLTs in another participant will not be automatically precluded from continued dosing during the safety review, and will be allowed to continue dosing for as long as tolerated unless directed otherwise as a result of the safety review by the DESC.

Dose escalation within individual participants will not be allowed. Refer to the *Participant Replacement during Dose Escalation/Safety Lead-in* section for definition of evaluable participants.

DLTs Requiring Discontinuation of Treatment

- If a study participant develops a grade 4 DLT after receiving cycle 1, then the study participant should be discontinued from treatment.
- If a study participant develops a grade ≥ 3 non-hematological AE that does not resolve to \leq grade 2 within 72 hours of onset, it should be considered a DLT and the study participant should be discontinued from treatment.
- If there is a delay in administration of the second cycle by > 4 weeks, it would result in discontinuation from treatment after discussion with the sponsor.

Study Enrollment Interruption:

Study enrollment will be temporarily interrupted pending review of the following:

- Any death that is not related to disease progression occurring within 30 days of receiving ASP0739 and/or pembrolizumab
- Occurrence of 2 grade ≥ 4 DLTs in 2 study participants
- Any grade 4 hypersensitivity reaction/anaphylaxis

Participant Replacement during Dose Escalation/Safety Lead-in:

Participants may be replaced in the safety lead-in or dose escalation cohort if:

- Participant is discovered to have enrolled without fully satisfying eligibility criteria.
- Participant did not receive the planned dose in cycle 1 for reasons other than DLT.
- Participant has no DLT and withdraws from the study before the end of the DLT evaluation period.

The decision to replace participants will be made by the sponsor based on the above criteria.

Recommended Phase 2 Dose

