6.5 Dose Modification

Dose modifications of ASP0739 are not allowed at the individual participant level without prior consultation with the sponsor's medical monitor. Any participants who do not receive a subsequent dose within the scheduled time window in the schedules of assessments [[Table 1](#) and [Table 2](#)] can only resume treatment after discussion with the medical monitor.

Any participant experiencing a grade 3 AE after receiving a dose of ASP0739 may receive the subsequently scheduled dose of ASP0739 only after the observed grade 3 AE has resolved to grade 1; the subsequent dose of ASP0739 may be reduced by one dose level, either from 1×10^8 to 1×10^7 cells/dose or from 1×10^7 to 1×10^6 cells/dose.

Further treatment reduction/withdrawal can be implemented after discussion with the medical monitor, including for any clinically significant AEs affecting vital organs (e.g., cardiac events).

Refer to [[Sections 10.8](#) Appendix 8: Infusion Reaction Dose Modification and Treatment (Guidelines for ASP0739 and Pembrolizumab); [10.10](#) Appendix 10: Dose Modification and Toxicity Management for Immune-related Adverse Events; and [10.11](#) Appendix 11: Dose Modification and Toxicity Management of Infusion Reactions Related to Pembrolizumab] and the approved pembrolizumab package insert, summary of product characteristics monograph or local product information supplied by the manufacturer for the recommended treatment modifications for pembrolizumab.

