9.3 Populations for Analyses

The following populations are defined:

Population	Description
Enrolled	All participants who sign the informed consent form are allocated to treatment
Full Analysis Set (FAS)	All participants who are enrolled and receive at least 1 dose of study treatment.
Response Analysis Set (RAS)	The response analysis set will consist of all participants who are enrolled and receive at least 1 dose of IP and have at least 1 post baseline primary efficacy measurement.
Safety Analysis Set (SAF)	All participants who take at least one dose of IP.
Pharmacokinetic analysis set (PKAS)	The PKAS consists of the administered population for which pharmacokinetics data are available for at least 1 time point. Additional participants may be excluded from the PKAS at the discretion of the pharmacokineticist.
Pharmacodynamic analysis set (PDAS)	The PDAS will include the participants from the administered population for whom sufficient pharmacodynamic measurements were collected. The PDAS will be used for all analyses of pharmacodynamic data.
DLT Evaluation Analysis Set (DEAS)	The DEAS is defined as all participants in the SAF by excluding participants who meet any of the following criteria: Participant is discovered to have enrolled without fully satisfying eligibility criteria. Participant received less than the planned dose in cycle 1 for reasons other than DLT. Participant has no DLT and withdraws from the study before the end of the DLT evaluation period. The DEAS will be used for the analysis of DLT data.

DLT: dose limiting toxicity

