Grade 2 Requires therapy or infusion interruption but responds promptly to symptomatic treatment (e.g., antihistamines, NSAIDs, narcotics, intravenous fluids); prophylactic medications indicated for \leq 24 hours.	
Stop Infusion.Additional appropriate medical therapy may include but is not limited to:
Intravenous fluidsAntihistaminesNSAIDsAcetaminophenNarcoticsIncrease monitoring of vital signs as medically indicated until the participant is deemed medically stable in the opinion of the investigator.If symptoms resolve within 1 hr of stopping drug infusion, the infusion may be restarted at 50% of the original infusion rate (e.g., from 100 mL/hr. to 50 mL/hr.). Otherwise, dosing will be held until symptoms resolve and the participant should be premedicated for the next scheduled dose. 
Participants who develop grade 2 toxicity despite adequate premedication should be permanently discontinued from further treatment (pembrolizumab only)
	
Pembrolizumab only: Participant may be premedicated 1.5 hours (\pm 30 min) prior to infusion of pembrolizumab with: Diphenhydramine 50 mg po (or equivalent dose of antihistamine). Acetaminophen 500 to 1000 mg po (or equivalent dose of analgesic).
 
Contact the study medical monitor regarding ASP0739 dose management

Table continued on next page

NCI-CTCAE Grade	Treatment	Premedication at Subsequent Dosing

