Grades 3 or 4 Grade 3: Prolonged (i.e., not rapidly responsive to symptomatic medication and/or brief interruption of infusion); recurrence of symptoms following initial improvement; hospitalization indicated for other clinical sequelae (e.g., renal impairment, pulmonary infiltrates) Grade 4: Life-threatening; pressor or ventilator support indicated	
 Stop Infusion. Additional appropriate medical therapy may include, but is not limited to: 
 Epinephrine* Intravenous fluids Antihistamines NSAIDs Acetaminophen Narcotics Oxygen Pressors Corticosteroids Increase monitoring of vital signs as medically indicated until the participant is deemed medically stable in the opinion of the investigator. Once the participant has been stabilized, collect blood for cytokine/chemokine panel (ad hoc collection for shipment to central lab). If the reaction is suggestive of anaphylaxis, collect blood (standard red top tube) for serum total tryptase level (levels typically peak within 3 hours after the onset of symptoms). Serum should be frozen if the assay cannot be performed promptly at the local laboratory. Hospitalization may be indicated. 
* In cases of anaphylaxis, epinephrine should be used immediately. Participant is permanently discontinued from further study drug treatment.
	Any grade 4 hypersensitivity reaction/anaphylaxis, study treatment should be discontinued

Appropriate resuscitation equipment should be available at the bedside and a physician readily available during the period of drug administration. For further information, please refer to the Common Terminology Criteria for Adverse Events v5.0 (CTCAE) at <http://ctep.cancer.gov>.

hr: hour; NCI: National Cancer Institute; NSAID: non-steroidal anti-inflammatory drug; po: by mouth

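### The single-agent DLT list lacks the combination list's item for a reaction that ends the infusion, so an ASP0739 reaction that stops the cycle 1 dose may go uncounted in BOIN

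*Protocol*

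**What the plan says.** Protocol Section 4.1 has two DLT lists. The combination list applies to events at least possibly related to ASP0739, pembrolizumab or both, and its last item is "Infusion-related reaction that requires the infusion to be discontinued". The single-agent list covers "any of the following events that occur within 28 days starting with the first dose on C1D1 in the dose escalation cohort" and has no counterpart. Its general non-hematological item needs grade 3 or higher with no fall to grade 2 or lower within 72 hours. The only infusion wording in that part exempts a managed grade 3 infusion-site reaction. An irAE of grade 3 or lower is exempt if it reaches grade 1 or lower "within 72 hours of onset after starting treatment including corticosteroids". SAP Section 5.2.1.1 refers back to Protocol 4.1 and adds nothing.

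Appendix 8 (Table 14) manages infusion reactions to both products:

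- **Grade 2:** the infusion is stopped and may restart at half rate if symptoms resolve within 1 hour. "Otherwise, dosing will be held until symptoms resolve and the participant should be premedicated for the next scheduled dose". The adjoining column refers ASP0739 dose management to the medical monitor.
- **Grades 3 and 4:** the infusion is stopped. The cell ends with "Participant is permanently discontinued from further study drug treatment", directly after a note on anaphylaxis.

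Section 6.5, by contrast, says that after a grade 3 AE a participant "may receive the subsequently scheduled dose of ASP0739 only after the observed grade 3 AE has resolved to grade 1".

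Section 4.1 allows replacement when "Participant did not receive the planned dose in cycle 1 for reasons other than DLT". The DLT analysis set (DEAS; Protocol Section 9.3, repeated in SAP Section 4) excludes a participant when "Participant received less than the planned dose in cycle 1 for reasons other than DLT".

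**The concern.** The same ASP0739-related event is dose-limiting in one cohort and can go uncounted in the cohort that sets the single-agent MTD, which caps the RP2D. Section 2.3.1.1 lists infusion-related reactions and cytokine release as potential ASP0739 risks, so the item is not relevant to pembrolizumab alone.

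An uncounted participant can also leave the denominator, because an incomplete cycle 1 dose without a DLT permits replacement. The step at stake is tenfold, from 1×10^7 to 1×10^8 cells. The DESC paragraph of Section 4.1 bases the next cohort's dose on BOIN and allows a choice more conservative than the BOIN MTD only when the RP2D is set. The automatic enrollment pause covers grade 4 hypersensitivity or anaphylaxis, non-progression deaths within 30 days, and two grade 4 or higher DLTs. It does not cover a grade 3 infusion reaction that settles.

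**Working it through.** **1. The plan's own rule.** Section 4.1 gives a target DLT rate of 0.30 and an interval of (0.236, 0.359). I assumed the usual BOIN multipliers, which the documents do not state: φ = 0.30, φ1 = 0.6φ = 0.18, φ2 = 1.4φ = 0.42.

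- λe = ln(0.82/0.70) / ln[(0.30×0.82)/(0.18×0.70)] = 0.2365
- λd = ln(0.70/0.58) / ln[(0.42×0.70)/(0.30×0.58)] = 0.3585

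These agree with the stated interval, and every cell for 3 to 8 participants is reproduced. The arithmetic is sound. The question is which events enter it.

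**2. Which reactions can go uncounted.**

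- *Grade 3, at grade 2 or lower within 72 h.* The general item is not met. If the reaction is classed as an irAE, it must also reach grade 1 or lower within the stated days to escape. If Table 14 ends treatment, cycle 2 never starts, which might be read as the item for a cycle 2 delay of more than 2 weeks. If Section 6.5 governs, cycle 2 can start on time and that item is not met.
- *Grade 2, cycle 1 dose never completed.* No item is met unless the event is called an autoimmune reaction or delays cycle 2 by more than 2 weeks.
- *Grade 4, or still grade 3 or higher at 72 h.* Outside this point.

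**3. Effect on the table, with no rate assumed and no other DLT.** One such reaction among 4 treated, with that participant replaced, reads 0/3: escalate. Counted, it reads 1/4: stay (1/3 is also stay). With 6 to 8 evaluable, one counted reaction alone would still escalate, but one other DLT plus one such reaction moves 1 (escalate) to 2 (stay).

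**4. Effect over assumed rates.** Let o be the rate of other DLTs and r the rate of infusion-ending reactions that meet no other item, independent of each other.

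- As written, a participant with such a reaction and no other DLT is excluded and replaced: p_w = o / [o + (1−o)(1−r)].
- Counted: p_c = 1 − (1−o)(1−r).
- P(escalate after 3 evaluable) = (1−p)³.

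With o = 0.10:

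| r | p_w | as written | p_c | counted | gap |
|---|---|---|---|---|---|
| 1% | 0.1/0.991 = 0.1009 | 0.727 | 0.109 | 0.707 | 0.02 |
| 2% | 0.1/0.982 = 0.1018 | 0.725 | 0.118 | 0.686 | 0.04 |
| 5% | 0.1/0.955 = 0.1047 | 0.718 | 0.145 | 0.625 | 0.09 |
| 10% | 0.1/0.910 = 0.1099 | 0.705 | 0.190 | 0.531 | 0.17 |

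**5. How wide the exposure is.** Section 6.1.1 gives about 50 mL at 4 to 6 mL/min, so the infusion lasts 50/6 = 8.3 to 50/4 = 12.5 minutes. Only a reaction starting in that window can cut the dose short. Section 2.3.1.1 reports no DLTs or safety concerns in the first 4 participants. Zero of 4 has a two-sided 95% upper limit of 1 − 0.025^(1/4) = 0.60, so it rules out little.

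**The case against.** The strongest case against is that the lists are regimen-specific by design. The infusion item closes a run with pneumonitis, neurological and myasthenic items that are also absent from the single-agent list and broadly match pembrolizumab toxicities. That is a plausible origin. However, the item is not limited to pembrolizumab, relatedness to ASP0739 alone is enough, and no reason for leaving it out of the single-agent list is given.

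A reader might infer that any grade 2 reaction lasting more than an hour loses the cycle 1 dose without being counted. The documents do not support that. Table 14 describes grade 2 as responding promptly and a reaction that does not as grade 3. It holds dosing only until symptoms resolve, so the dose might still be finished, and it sends ASP0739 dosing to the medical monitor. The grade 2 case is real but thin.

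The grade 3 case is arguable too, as step 2 shows. The permanent-discontinuation sentence may refer only to anaphylaxis, and the cycle 2 delay or irAE items might capture the event.

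Safeguards also stand. The DESC confirms DLTs and considers all safety findings, replacement is optional, and SAP Section 6.5.3 tabulates infusion reactions as AEs of special interest. Protocol Sections 2.3.2 and 9.5, and the starting-dose paragraph of 4.1, let wider safety data weigh on the next dose, although the DESC paragraph is stricter. No infusion reaction or cytokine release was seen non-clinically. The SAP Introduction reports early termination with no combination treatment, so the cohort with the stricter list never ran.

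**Conclusion.** The gap exists and is minor. It rests mainly on a grade 3 ASP0739 reaction that stops the cycle 1 infusion and settles within 72 hours, and on reading the irAE and delay items as not catching it. One such event is enough to turn a first-cohort stay into an escalation. How often that would happen is unknown, because the documents give no reaction rate. Under 10% other DLTs, independence and replacement, the loss of protection is negligible at 1-2%, modest at 5% and material only near 10%. Here r is narrower than the overall infusion-reaction rate.

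Three stronger readings go too far:

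- *The DEAS exclusion itself drives the wrong action.* It does not: with the event not counted as a DLT, 0/3 and 0/4 both escalate. The missing DLT item is what matters.
- *The plan hides infusion reactions, or the MTD is shown to be unsafe.* The reactions are reported and reviewed, and nothing in the documents shows that one was missed.
- *The Japanese safety lead-in has the same gap.* It has no DLT list of its own, and the single-agent list is worded for the dose escalation cohort, so applying it there is an inference.

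**What to change.** Add to the single-agent DLT list the combination item "Infusion-related reaction that requires the infusion to be discontinued", worded for ASP0739 and limited to a permanent stop that leaves the planned cycle 1 dose incomplete. That limit keeps out grade 2 reactions after which the dose is finished. Also state whether Appendix 8 (Table 14) or Section 6.5 governs a grade 3 ASP0739 reaction.

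For the terminated study, add one SAP listing of any cycle 1 dose cut short by an IP-related AE, with its DEAS flag, and show the DLT count with and without it. Much of this is already planned as exposure, AE and analysis-set output; the cross-reference is what is new.

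The cost is one protocol line, one clarifying sentence and one listing, with no new data collected. The downside is that a dose may occasionally be held or lowered for a manageable reaction.
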